### **4. SAE REPORTING**

The Investigator has the responsibility of reporting SAE/SADE to the Sponsor/CRO immediately and in any case no later than 24 hours of becoming aware by using the **SAE/SADE Reporting Form**, accompanied by the **SAE/SADE Reporting Form Instructions**.

The sponsor shall implement and maintain a system to ensure that the reporting of the reportable events, as above defined, is provided by the investigator to the sponsor immediately, but not later than 3 calendar days after the investigation site study personnel's awareness of the event.

The Sponsor must perform the evaluation of each SAE in order to assess of Seriousness, Expectedness and causality relationship to the Investigational Medical device (IMD) and/or the procedure.

The Sponsor must report to all NCAs where the clinical investigation is authorized to start:

- a) any serious adverse event that has a causal relationship with the investigational device, the comparator or the investigation procedure or where a such causal relationship is reasonably possible;
- b) any device deficiency that might have led to a serious adverse event if appropriate action had not been taken, intervention had not occurred, or circumstances had been less fortunate;
- c) any new findings in relation to any event referred to in points a) and b).

For all reportable events as described above which indicate an imminent risk of death, serious injury, or serious illness and that requires prompt remedial action for other patients/subjects, users or other persons or a new finding to it: **Immediately, but not later than 2 calendar days** after awareness by the sponsor of a new reportable event or new information in relation with an already reported event. This includes events that are of significant and unexpected nature such that they become alarming as a potential public health hazard. It also includes the possibility of multiple deaths occurring at short intervals. These concerns may be identified by either the NCA or the manufacturer.

Any other reportable events or a new finding/update to it: **Immediately, but not later than 7 calendar days** following the date of awareness by the Sponsor of the new reportable event or new information in relation to the already reported event.

According to article 80 of Regulation 745/2017/EU, the sponsor shall fully record all of the following:

- (a) any adverse event of a type identified in the clinical investigation plan as being critical to the evaluation of the results of that clinical investigation;
- (b) any serious adverse event;
- (c) any device deficiency that might have led to a serious adverse event if appropriate action had not been taken, intervention had not occurred, or circumstances had been less fortunate;
- (d) any new findings in relation to any event referred to in points (a) to (c) furthermore.

#### Reporting form

The reporting form is study specific and covers only a given clinical investigation, defined by a distinct clinical investigation plan. The table gives a cumulative overview of the reportable events per clinical investigation and will be updated and transmitted to participating NCAs each time a new reportable event or a new finding to an already reported event is to be reported.

The sponsor shall report, without delay to all Member States in which the clinical investigation is being conducted, all of the following by means of the electronic system, if any:

- (a)any serious adverse event that has a causal relationship with the investigational device, the comparator or the investigation procedure or where a such causal relationship is reasonably possible;
- (b) any device deficiency that might have led to a serious adverse event if appropriate action had not been taken, intervention had not occurred, or circumstances had been less fortunate;
- (c) any new findings in relation to any event referred to in points (a) and (b).

Copies of any reports to regulatory bodies regarding serious and unexpected AEs will be provided to the investigators for review and submission to the EC. The communication of any SAEs to the EC and Competent Authority, will be done according to national requirements in Romania by the Investigator). Copies of SAEs correspondence with the investigators, regulatory bodies, and Sponsor must be retained with study records.

### **3.7. DATA COLLECTION**

#### **3.7.1. Collected variables**

The details and template of the questionnaires are reported in Annex 3 with the corresponding references. Moreover, the questionnaires are contained in the CRF section of the ISF/TMF, as a separate document. The data collected will be saved on databases corresponding to the sites. Each database will be uniquely identified with the name of the location; each investigator will input data only in the database allocated to his location.

#### **3.7.2. Schedule of assessments by visit**

##### **SCHEDULE OF ASSESSMENTS**

Procedures	Visit 1	Visit 2	Follow up call
	Screening Baseline		Follow up visit
	Day 0	Day 14 (± 2)	Day 30 (± 1)
Informed consent	X		
Inclusion Criteria	X		
Exclusion Criteria	X		
Demographics and Medical History	X		
Physical examination and Vital signs 	X	X	
Concomitant treatments and medications assessment	X	X	X
Short Health Scale for Haemorrhoidal Disease (SHS HD ) (by patient)	X	X	
Haemorrhoid Severity Score (HSS) (by Investigator)	X	X	
Haemorrhoidal Disease Symptom Score (HDSS) (by patient)	X	X	
Compliance		X	X

Patient Diary supply	X		
Patient Diary collection		X	
MD supply	X		
MD collection		X	
AE / ADE / DD assessment	X	X	X

Patients diagnosed with Grade I – II symptomatic haemorrhoids (according to Goligher classification) confirmed by clinical and anoscopic or proctoscopic examination performed within 3 months before baseline will be enrolled. Haemorrhoids evaluation, pulse, blood pressure (diastolic and systolic), weight / height and BMI (kg/m^2) will be collected.

### 3.7.2.1. Study visits

#### Visit 1 Screening / Baseline Visit (day 0)

At each Centre, patients will be enrolled consecutively. During this visit, patients who will meet the eligibility criteria (inclusion and exclusion criteria) will be enrolled after the signature of the informed consent form and will be informed verbally and in writing about the nature and requirements of the trial. Patients agreeing with the participation in the study will have to date and sign the informed consent form prior to any study-related procedure. All the screening procedures must be completed during this visit.

During this visit, the Investigator will collect information regarding medical history, demography, concomitant treatments and medications, AE/SAE if applicable. The Investigator will report data on the appropriate eCRF pages.

A physical examination will be performed, including evaluations of vital signs; pulse, blood pressure (diastolic and systolic), weight / height and BMI (kg/m^2) data will be collected. An evaluation of the haemorrhoidal disease will be performed, and a confirmation of the diagnosis and of the stage of haemorrhoids will take place, according to inclusion criteria (patients diagnosed with Grade I – II symptomatic haemorrhoids (according to Goligher classification, confirmed by clinical and anoscopic or proctoscopic examination performed within 3 months before baseline)

During this visit the following questionnaires will have to be completed:

- **HR-QoL questionnaire: SHSHD (by patient)**
- **HSS (by Investigator)**
- **HDSS (by patient)**

During this visit, the MD will be provided to each patient. The used, partially used and unused containers of the MD will have to be brought back to the centre on the last study visit. The MD will be supplied in the same package available on the market, and with the same leaflet / IFU – Instructions for Use.

A patient diary will be supplied; it will have to be completed at home by patients for the whole duration of the study. A series of information will have to be collected related to the health status of the patient (not an exhaustive list): use of any treatment or OTC or prescribed medications (concomitant treatments and medications), start and stop dates and name/dosage of the product will be collected; AE/ADE/DD occurrence; self-administration of the MD (according to IFU and standard clinical practice).

The importance of duly completing the diary will be stressed by the Investigator. The completed diary will be collected at the end of the study (at V2). Patients will be advised to note any major modification to their diet

and / or lifestyle in the diary. Moreover, patients will be informed (it will be written in the diary) that they will receive a phone call from the investigator 30 days after the end of the study to check if there have been AEs. The following visit (V2) will be scheduled 14 ( $\pm$  2) days after V1; a phone call will be scheduled 30( $\pm$  1) days after V1.

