	
from pain, burning, itching and other related complaints, contributing to the physiological restoration of the anal and perianal tissues. Its application leaves the treated area soft and moisturised, avoiding the onset of irritation and cracking of the skin. The lubricating action helps to facilitate bowel movement, thus minimising the trauma and pain sensation associated with defecation.
 
PROCTOEZE® PLUS key ingredients are mainly paraffinum liquidum, petrolatum, dimethicone, and hydroxyethylcellulose.
 
All the patients will use the MD PROCTOEZE® PLUS during the whole study according to Instruction for Use of the MD and to standard clinical practice.

Chronogram of visits	
The study envisages the following visits and phone follow up per patient:
 
 
• Visit 1, day 0: Screening / Baseline visit.
 
• Visit 2, day 14 (<math>\pm</math> 2 days):
 
• Phone follow up, day 30 (<math>\pm</math> 1 day).
 

Study duration	The study will last 30 days for each patient.

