Procedures	
Visit 1 Screening / Baseline visit (day 0)
 
 
• Informed consent / Eligibility Criteria
 
• Demographics / Medical History / Physical examination and vital signs (including haemorrhoids evaluation and confirmation of diagnosis)
 
• Concomitant treatments and medications assessment
 
• Quality of life assessment by means of the Short Health Scale for Haemorrhoidal Disease (SHSHD) by patient
 
• Haemorrhoid Severity Score (HSS) by Investigator
 
• Haemorrhoidal Disease Symptom Score (HDSS) by patient
 
• Diary supply
 
• MD supply
 
 
Visit 2 End of Study visit (day 14 <math>\pm</math> 2 days)
 
 
• Treatment adherence
 
• Diary's maintenance
 
• Physical examination and vital signs (including haemorrhoids evaluation)
 
• Concomitant treatments and medications assessment
 
• Quality of life assessment by means of the Short Health Scale for Haemorrhoidal Disease (SHSHD) by patient
 
• Haemorrhoid Severity Score (HSS) by Investigator
 
• Haemorrhoidal Disease Symptom Score (HDSS) by patient
 
• Diary collection
 
• MD collection
 
• Safety assessment by AE / ADE / DD collection
 
 
Phone call (day 30 <math>\pm</math> 1 day)
 
 
• Treatment adherence
 
• Diary's maintenance
 
• Safety assessment by AE / ADE / DD collection
 

Not allowed concomitant treatment or	Any drug or treatment mentioned in the eligibility criteria as not allowed will be forbidden during the study and its use will have to be avoided by patients, otherwise they are excluded from the participation: use of laser treatment,

medications	
steroidal or non-steroidal anti-inflammatory drugs, analgesics, any anti-haemorrhoidal treatment (both drugs and dietary supplements), anticoagulants, and antiplatelet agents will be not allowed during the whole study.
 
No restriction on treatments taken previously by patients for medical conditions not related to this study protocol will be envisaged.
 
Patients will be advised to note any concomitant treatment or medications or any major modification to their diet and / or lifestyle in the diary.

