### **3. TIME PERIOD AND FREQUENCY FOR EVENT ASSESSMENT AND FOLLOW-UP**

The occurrence of an adverse event (AE) or serious adverse event (SAE) may come to the attention of study personnel during study visits and interviews of a study participant presenting for medical care. At each visit/assessment, the participant should be assessed for the possible occurrence of an AE/SAE. Care will be taken not to introduce bias when detecting adverse events and/or SAEs. Open-ended and non-leading verbal questioning of the participant is the preferred method to inquire about adverse event occurrences.

Any medical condition that is present at the time that the participant is screened will be considered a baseline and not reported as an AE. However, if the study participant's condition deteriorates at any time during the study, it will be recorded as an AE. Changes in the severity of an AE will be documented to allow an assessment of the duration of the event at each level of severity to be performed. AEs characterized as intermittent require documentation of the onset and duration of each episode.

AE/SAE can occur during any period of the study. The Investigator will record all reportable events with start dates occurring any time after informed consent is obtained until 7 (for non-serious AEs) or 30 days (for SAEs) after the last day of study participation. At each study visit, the investigator will inquire about the occurrence of AE/SAEs since the last visit. Each patient will receive a phone call from the investigator 30 days after the end of the study to check if there have been AEs. Events will be followed for outcome information until resolution or stabilization.

AE/SAE, as all medical occurrences, should be recorded by the Investigator in the subject's medical records as source data.

Each identified AE is assessed by the Investigator for Seriousness and Causality relationships to the Investigational Medical device or procedure.

All AE/SAE will be recorded on the appropriate case report form (CRF) by the Investigator.

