#### Visit 2 (day 14 $\pm$ 2 days)

During this visit, the Investigator will perform the following examinations and the e-CRF will be completed accordingly:

- Physical examination (according to what was already performed at visit 1: pulse, blood pressure, weight / height and BMI will be evaluated), including haemorrhoidal disease evaluation.
- Concomitant treatments and medications assessment.
- Evaluation of compliance (MD administration assessment by means of the patient's diary carried out by Investigator).
- Diary and MD (used, partially used, or unused containers) collection.
- Safety assessment by AE/ADE/DD collection.

During this visit the following questionnaires will have to be completed:

- HR-QoL questionnaire: SHSHD (by patient)
- HSS (by Investigator)
- HDSS (by patient)

Patients who discontinued the protocol, will be visited reporting on the last visit page all the safety assessments and (if possible) the examinations and questionnaires requested for the last visit.

Patients who discontinued the protocol, will be visited reporting on the last visit page all the safety assessments and (if possible) the questionnaires requested for the last visit.

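### The safety call is promised 30 days after the end of the study but scheduled at day 30 after Visit 1, so the 30-day SAE window outlasts the last scheduled contact

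*Combined protocol and SAP*

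**What the plan says.** The protocol gives two timings for one safety call.

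- **Relative to the end of the study.** Section 3.6.2, item 3 (time period and frequency for event assessment) says "Each patient will receive a phone call from the investigator 30 days after the end of the study". Section 3.7.2.1, under Visit 1, gives patients the same commitment: "they will receive a phone call from the investigator 30 days after the end of the study to check if there have been AEs".
- **Relative to Visit 1.** The next sentence of section 3.7.2.1 says "a phone call will be scheduled 30" (±1) days after Visit 1. The Synopsis (chronogram and procedures), both Schedule of Assessments tables and the phone-call paragraph of section 3.7.2.1 also give day 30 ± 1.

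Section 3.6.2, item 3 records events "until 7 (for non-serious AEs) or 30 days (for SAEs) after the last day of study participation".

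The last day of participation is not defined, and the text points two ways. The Synopsis procedures name the day-14 visit "Visit 2 End of Study visit". Section 3.7.2.1 says "The completed diary will be collected at the end of the study (at V2"), and its Visit 2 list includes "Diary and MD (used, partially used, or unused containers) collection". The Synopsis entry on study duration says "The study will last 30 days for each patient".

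**The concern.** A call timed from the end of the study would close the SAE window. A call timed from Visit 1 does not. On the scheduled timing, the final part of a window that the protocol set for itself depends on patients or their carers coming forward, or on an event reaching the site by another route.

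Safety is a stated objective, and the report draws a conclusion from it. The Results in the Summary state that no events occurred. The Executive summary and the Discussion then present the device as having been shown to be well tolerated. The report gives neither the length of follow-up nor the number of patients reached by the call. The safety-outcome table planned in section 4.3.2 is not among Tables 1 to 7.3. A reader cannot tell how much observation lies behind the zero.

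**Working it through.** **Inputs, counted from Visit 1 = day 0**
- Visit 2: day 14 ± 2, so day 12 to 16 (Schedule of Assessments).
- Call: day 30 ± 1, so day 29 to 31 (Schedule of Assessments).
- Recording windows: last day of participation + 7 days for non-serious AEs, + 30 days for SAEs (section 3.6.2, item 3).

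**1. Can the promise reproduce the scheduled day?** Promised call day = end of study + 30.
- End at Visit 2: 14 + 30 = day 44 (12 + 30 = 42 to 16 + 30 = 46).
- End at day 30: 30 + 30 = day 60.
- A result of day 30 would need the study to end on day 0.

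Neither reading gives the scheduled day.

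**2. Participation ends at Visit 2.** Days without scheduled contact = SAE window end − call day.
- Nominal: 44 − 30 = 14 days, 14/30 = 47% of the window.
- Minimum: 42 − 31 = 11 days, 11/30 = 37%.
- Maximum: 46 − 29 = 17 days, 17/30 = 57%.
- Non-serious AE window: closes at day 12 + 7 = 19 to 16 + 7 = 23, before the call at day 29 to 31, so it is covered.

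**3. Participation ends at day 30.** The call is then the last contact. All 30 SAE days and all 7 non-serious AE days come after it.

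**4. What zero events can support.** Exact two-sided 95% upper limit for 0 of n = 1 − 0.025^(1/n). With n = 50: 1 − 0.025^(1/50) = 7.1%. The number reached by the call is not reported. If it were 45 or 40 (assumed values), the limit would be 7.9% or 8.8%.

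**The case against.** The strongest reply is that day 30 is plainly the intended timing. All the schedules agree, so a site following them would call on day 30, and the two sentences that differ are a wording slip. Much of this stands. The visible diary instructions do not carry the promise and the consent pages are not available, so what patients were actually told is unknown. Section 3.6.2 sets a duty to record events, not a duty to contact patients to the end of the window. It allows events to surface when a participant presents for care, and it follows them to resolution. The reply does not close the point, because with day 30 accepted the SAE window still outlasts the last planned contact.

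One could also suppose that two calls were meant. The schedules and the CRF provide for one only.

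The 14-day figure depends on participation ending at Visit 2, which is disputable. The endpoints and inclusion criteria speak of day 30, and the day-30 call includes a compliance check. On that reading the 14 days do not apply, and the statement that the whole window is uncovered largely follows from the window starting when participation ends.

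A reader might infer from the calendar that follow-up was cut short. The last patient entered on 17 December 2024. Visit 2 + 30 days for that patient falls between 28 January and 1 February 2025, after the study stop date of 27 January. The documents do not support that inference. They do not define the stop date, section 3.6.2 does not end SAE recording there, and nothing shows when calls were made.

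The missing safety table and the tolerability wording would need attention even with a correctly timed call, so they do not add to the weight of the timing conflict.

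**Conclusion.** The conflict is real, and neither definition of the end of participation removes it. If participation ends at Visit 2, 14 days of the SAE window (11 to 17) have no scheduled contact. If it ends at day 30, the whole window follows the last contact. These figures assume that visits and calls fall within their stated limits.

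The gap is in scheduled contact only. It would be wrong to conclude that SAEs in those days could not be recorded, that any were missed, or that the reported zero is incorrect. On the Visit 2 reading the non-serious AE window is covered. The primary analysis is unaffected. Severity is minor to moderate.

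**What to change.** **Protocol**
- State one last day of participation, consistent with the end of treatment. Use Visit 2 if treatment ends at day 14, as the collection of diary and device implies; otherwise use day 30. The sponsor has to settle this before moving the call.
- Schedule the call 30 days (0 to +2) after that day, so that it never precedes the close of the SAE window.
- Align the Synopsis (chronogram, study duration, procedures), both Schedule of Assessments tables, section 3.6.2 item 3 and section 3.7.2.1.
- If Visit 2 is chosen, also align the day-30 wording in the Summary endpoints and selection criteria, the Synopsis outcomes and inclusion criteria, and sections 3.3.1 and 3.5.1. If day 30 is chosen, the call falls at about day 60, and the end-of-study label and the collections at Visit 2 must change.

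**Cost on the Visit 2 reading**
- The call moves to day 42 to 48 (42 + 0 to 46 + 2), which is 12 to 18 days after nominal day 30.
- It comes 23 to 25 days after the non-serious AE window closes (30 − 7 to 32 − 7). Now it comes 6 to 12 days after (29 − 23 to 31 − 19). Recall of non-serious events and device deficiencies is therefore later.
- The day-30 adherence check moves with it. Keeping a brief day-30 call as well avoids these last two costs, at the price of one extra contact.

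**Report**
- Add the safety table planned in section 4.3.2, with the number of patients reached by the call and the follow-up covered. The CRF has a field for the call date (Visit 3, call visit).
- In the Executive summary and the Discussion, replace the tolerability claim with: *No events were observed in n patients followed to day X (exact two-sided 95% upper limit 7.1% if n = 50).* Fill in n and X from the call dates, and recompute the limit if n is below 50.

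This is one small table and one changed sentence in each of the two places.

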#### Visit 2 (day 14 $\pm$ 2 days)

During this visit, the Investigator will perform the following examinations and the e-CRF will be completed accordingly:

- Physical examination (according to what was already performed at visit 1: pulse, blood pressure, weight / height and BMI will be evaluated), including haemorrhoidal disease evaluation.
- Concomitant treatments and medications assessment.
- Evaluation of compliance (MD administration assessment by means of the patient's diary carried out by Investigator).
- Diary and MD (used, partially used, or unused containers) collection.
- Safety assessment by AE/ADE/DD collection.

During this visit the following questionnaires will have to be completed:

- HR-QoL questionnaire: SHSHD (by patient)
- HSS (by Investigator)
- HDSS (by patient)

Patients who discontinued the protocol, will be visited reporting on the last visit page all the safety assessments and (if possible) the examinations and questionnaires requested for the last visit.

Patients who discontinued the protocol, will be visited reporting on the last visit page all the safety assessments and (if possible) the questionnaires requested for the last visit.

